6 STUDY INTERVENTIONS

6.1 Study Device

The BD Nexiva closed IV catheter systems are intended to be inserted into a patient's vascular system for short term use to sample blood, monitor blood pressure, or administer fluids. These devices may be used for any patient population with consideration given to adequacy of vascular anatomy, procedure being performed, fluids being infused, and duration of therapy.

BD Nexiva closed IV catheter systems are over-the-needle, intravascular (IV) catheters. These devices have a radiopaque BD Vialon catheter, needle, needle shield, septum, stabilization platform, integrated extension tubing, clamp, Luer adapter, and vent plug. The needle and catheter are protected by a needle cover

The closed system is designed to keep blood contained within the device throughout the insertion process. The septum is designed to wipe visible blood from the needle surface as the needle is withdrawn from the catheter, further reducing the risk of blood exposure. The needle tip is passively protected when the needle is removed, reducing the risk of accidental needlestick injury.

These devices have BD Instaflash™ Needle Technology, allowing for immediate visualization of blood along the catheter.

Continuous blood return is seen in the extension tubing. The vent plug prevents blood leakage from the extension tubing during insertion. Both the stabilization platform and Luer connector are color coded to

indicate catheter gauge size (24 GA (0.7 mm) = Yellow, 22 GA (0.9 mm) = Blue, 20 GA (1.1 mm) = Pink, 18 GA (1.3 mm) = Green).

See the IFU included in the Appendix (16.1) for full details on the device.

6.2 Control Device/Standard of Care

Not applicable; this is a single-arm study.

6.3 Ancillary Devices/Products

The details of the ancillary devices/products that are critical to the use of the study device and/or execution of the protocol (e.g., device/procedure components that are used with the study device) are provided in Table 2 below.

Table 1. Ancillary products

Description	Manufacturer
3M™ Tegaderm™ IV Securement Dressing, Nexiva or equivalent	3M
BD MaxZero™ Needleless Connector	BD
BD Vacutainer® Luer-Lok™ Access Device	BD
BD Vacutainer® EDTA, 2 mL	BD
BD Vacutainer® Citrate, 2.7 mL	BD
BD Vacutainer® EDTA, 6 mL	BD
BD PosiFlush™ SP Pre-filled Saline Syringe, 10 mL	BD
BD Vacutainer® UltraTouch™ push button blood collection set (21G) w/ holder	BD
Pressure Transducer, Model TNF-R	Argon Medical

Table 2. Ancillary devices-Data Acquisition

Description	Manufacturer
SG-Link Data Logger	Lord Corporation
WSDA Base station	Lord Corporation

Pressure Transducer DTX Interface Cable, Flying Leads	Merit Medical
Custom Graphical User Interface (GUI)	BD
Laptop Computer 
 • 7th Generation Intel® Core™ i7-7820HQ (Quad Core, 2.90Gz, 8MB cache) • Intel® Tri-Band Wireless-AC 18265 WiGig + Wi-Fi + BT4.2 Wireless Driver • 512GB Solid State Drive M.2 PCIe) • 32GB (2x16GB) DDR4 Memory 	Dell

The data acquisition system will be utilized to collect in-line fluid pressure measurements during catheter flush procedures. The data logger is used to acquire raw pressure data from the transducer and wirelessly transmit the data to the base station. The transducer is powered by the data logger via interface cable connection between the two components. Calibration of data logger will occur prior to use in the study to generate a calibration curve to translate bit values measured by the transducer directly to pressure data. The transceiver base station attaches to the computer via USB and provides the communication link between the data loggers and LabVIEW GUI software application. The LABVIEW based GUI application is loaded on the laptop computer and will be utilized to present the user with functions that allow initialization of data acquisition, real-time visualization of pressure data, and downloading data stored on internal memory.

6.4 Device Labeling

All products (Table 1) utilized in the protocol are commercially available in Australia. These products will be supplied as labeled by the manufacturer.

6.5 Treatment Allocation and Measures to Minimize Bias

The allocation of participants to a particular intervention (e.g., 20G or 22G) and randomization processes are described in the following sub-sections.

6.5.1 Randomization

Participants will be randomized using R statistical software*¹ (R 3.6.2 or higher). The generation of the randomization list will be conducted by a staff member not involved in data acquisition or analysis. Each randomization number will have a corresponding code (e.g., LA_20G_1.75 – indicating a Nexiva 20G 1.75

*¹ R Core Team. R: A Language and Environment for Statistical Computing. R Foundation for Statistical Computing, Vienna, Austria, 2016. URL <https://www.R-project.org/>.

will be first inserted into the left arm). The participant will then have the other length PIVC of the same gauge inserted into the contralateral arm.

Intervention kits will be created for each participant using large ziplock bags with all necessary (plus extra) consumables inside. Each kit will be separated via separate ziplock bags into consumables required for the right arm and left arm. Once the kits have been created, the appropriate randomization number will be recorded on the outside of each. Subsequently, the corresponding code will be placed in an envelope and sealed with the randomization number written on the outside of the envelope. These envelopes will be produced in duplicate with the second envelope sealed in a locked cabinet in the CTU for the circumstance where unblinding is required. Thereafter, the randomization list excluding the corresponding code will be given to the postdoctoral research fellow for storage until a randomization number is requested for the study.

6.5.2 Blinding/Masking

Due to the concealment of intervention allocation, most staff members, other than the inserter and study manager (research assistant), will be blinded to which gauge and length catheter the participant is receiving. To avoid bias sonographic data measurements (e.g., vessel diameter, C/V ratio, blood flow velocity) will be acquired on a separate day at the end of each working week. The acquisition of the sonographic measurements will be conducted by the sonographer). All concealed data will be transferred into an excel spreadsheet that will be subsequently grouped into 2 groups in a separate excel spreadsheet by a staff member not involved in data analysis and is unblinded. This will allow the researchers to analyze the data without having access to information about the allocation

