7.4 Image acquisition of indwelling catheter and cephalic vein

The insertion loci will be assessed prior to, and immediately after, insertion of the PIVC using clinically approved ultrasound with a wide-band, high frequency linear array probe from which all B-Mode, color-flow (CF), and pulse wave doppler (PWD) images will be acquired. At each visit prior to flushing and blood collection the following images will be recorded: a) three cross-sectional, B-mode images with the indwelling PIVC in view; b) three cross-sectional, B-mode images proximal to the PIVC tip; c) three longitudinal, B-mode images encompassing close to the insertion point of the PIVC to beyond the PIVC tip; and d) a 15 s longitudinal, PWD-CF duplex cine loop with the sample volume set ~1cm proximal to the PIVC tip. The sampling frequency for all images will be chosen high enough to avoid frequency aliasing. Coded harmonic imaging will be utilized for all images to improve visual clarity via enhancement of near-field resolution.

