7.4.2 Angle of insertion, catheter length in vessel

Calculation of the angle of insertion, and catheter length in vessel will be achieved via assessment of the three longitudinal, B-mode scans to be taken where the probe is positioned in-line with the superior surface of the PIVC tip. These measurements (superior and inferior angles) will be taken with the internal calculations of the clinically approved ultrasound. The data will be reported as the average of the values taken from the three images.

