7.4.3 Vessel diameter, C/V ratio

Calculation of the vessel diameter, and C/V ratio will be achieved via assessment of the three cross-sectional, B-mode scans to be taken with the indwelling tip PIVC in view. The vessel diameter and catheter diameter will be calculated from the horizontal axis using the internal calculations of the clinically approved ultrasound. The data will be reported as the average of the values taken from the three images.

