2.3.2 Blinding/Masking

Due to the concealment of intervention allocation, most staff members, other than the inserter and study manager (research assistant), will be blinded to which gauge and length catheter the participant is receiving. In order to avoid bias, sonographic data measurements (e.g., vessel diameter, C/V ratio, blood flow velocity) will be acquired on a separate day at the end of each working week. The acquisition of the sonographic measurements will be conducted by the sonographer). All concealed data will be transferred into an Excel spreadsheet that will be subsequently grouped into 2 groups in a separate Excel spreadsheet by a staff member not involved in data analysis and is unblinded. This will allow the researchers to analyze the data without having access to information about the allocation

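### The stated staff blinding to gauge and length is not delivered: coloured parts show gauge to staff who handle the device, and ultrasound shows in-vessel length to the sonographer

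*Protocol*

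**What the plan says.** Protocol 6.5.2 gives allocation concealment as the reason why most staff, "other than the inserter and study manager (research assistant), will be blinded to which gauge and length catheter" the participant has. SAP 2.3.2 repeats that these staff "will be blinded to which gauge and length catheter the participant is receiving". The mechanism offered is the sealed-envelope system of Protocol 6.5.1, together with sonographic measurement on a separate day and an analysis file without allocation information.

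Elsewhere the documents describe something different:

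- Protocol 6.1 says of the device: "Both the stabilization platform and Luer connector are color coded to" show gauge. The colours of the two study gauges are given as "22 GA (0.9 mm) = Blue, 20 GA (1.1 mm) = Pink".
- Protocol 7.4 requires "three longitudinal, B-mode images encompassing close to the insertion point of the PIVC to beyond the PIVC tip", and Protocol 7.4.2 says that "catheter length in vessel will be achieved via assessment of the three longitudinal, B-mode scans".
- The study is called open-label in the Protocol synopsis, Protocol 4.1, Protocol 10.1 and SAP 2.1.

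**The concern.** Concealing the allocation sequence protects the assignment up to insertion. It cannot hide a device that then stays on the arm for up to 72 hours and is accessed repeatedly. The blinding paragraph treats the first as if it secured the second.

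This bears most on the gauge comparison, which is between participants. The primary event is functional: a catheter fails when it can no longer be flushed or drawn from, as settled by working through a rescue decision tree (Protocol 7.6, SAP 6.6). The steps listed in SAP Table A.7.1 are manual (digital pressure, dressing replacement, tourniquets, heat packs), and how long staff persist can depend on what they expect. The expectation is written down: Protocol 3.2.1 predicts longer indwell for the larger bore. Fill time is taken by stopwatch (SAP 5.1.3) and the insertion site is scored by eye (Protocol 7.10.1), so both are open to the same influence. A report that repeated the blinding statement would claim a protection against this that the design does not supply.

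**Working it through.** The plan gives no figure for blinding, so there is none to reproduce. The check sets sections side by side and adds simple arithmetic.

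**Gauge at the bedside.** Gauge is on display in blue or pink on the platform and the Luer connector (Protocol 6.1). A nurse inspects the insertion site (Protocol 7.10.1), and the dressing and whole line (Protocol 7.10.2), before each draw. Flushes and draws go through a connector attached to the extension (Protocol 7.2 and 7.3). Luer tightening and dressing replacement are rescue steps (SAP Table A.7.1). No section describes hiding the coloured parts. The bandage in Protocol 2.3.1 is there to prevent catching, not to mask. With 7 sessions and 80 catheters there are at most 7 × 80 = 560 catheter accesses. That counts opportunities to see the colour if nothing fails; it is not a measure of bias.

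**Length at the bedside.** The colour code carries no information on length. Nothing in the documents shows length to someone who flushes or draws and is kept away from the scans.

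**Length at ultrasound.** Nominal lengths are 1 × 25.4 = 25.4 mm and 1.75 × 25.4 = 44.45 mm, a difference of 19.05 mm. What is measured is length in the vessel, not labelled length. Even so, apart from measurement error, a reading above 25.4 mm cannot come from a 1 inch catheter. Protocol 4.1 itself relies on the scans separating the lengths: after five participants the study may stop if tip positions are not distinct. Measuring on another day does not take this out of the image. Who the sonographer is remains unclear: Protocol 13.2 lists ultrasound training for the principal investigator and the research assistant, and Protocol 6.5.2 uses the latter title for the unblinded study manager.

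**Gauge in the analysis file.** Protocol 7.4.3 says "The vessel diameter and catheter diameter will be calculated from the horizontal axis using the internal calculations of the clinically approved ultrasound". SAP 5.1.5 instead takes catheter diameter from the specification: 0.90 mm for 22G and 1.10 mm for 20G. Under the SAP rule

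C/V ratio × vessel diameter = catheter diameter = 0.90 or 1.10 mm.

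At the 2.55 mm minimum vein:

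- 20G: 1.10 / 2.55 = 43.1%, and 0.431 × 2.55 = 1.10 mm.
- 22G: 0.90 / 2.55 = 35.3%, and 0.353 × 2.55 = 0.90 mm.

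A file holding both columns therefore identifies gauge apart from rounding and averaging, which are small against a 0.20 mm gap. Whoever computes the ratio by this rule must also know the gauge.

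**Possible size.** There are 20 catheters per configuration and 20 × 2 = 40 per gauge. One catheter reclassified at 72 hours moves patency by 1/20 = 5 points in its configuration, or 1/40 = 2.5 points in its gauge group. These are upper bounds per catheter. One kept going at 24 hours that fails at 30 hours adds 6 hours of indwell and leaves 72-hour patency unchanged. The documents do not say how many decisions would be borderline, so no total can be given.

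**The case against.** The best defence is that the study is openly declared open-label and that the paragraph says only most staff, with two named exceptions. The documents do not name who flushes, draws or times the fill. If the study manager does so, the sentence is not contradicted for the primary event. That stands as a reading of the sentence. It does not rescue the protection, because the failure decision would then be made by someone the plan itself lists as unblinded.

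Several further points stand and limit the concern. Length is the paired comparison and the main rationale, and bedside staff could remain unaware of it. cfHb and AU480 results are instrument readings. Allocation concealment before insertion is intact. Failure is decided through a predefined tree, and remediation attempts are tabulated by device, so unequal persistence can be examined. This is a feasibility study without acceptance criteria.

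A reader might infer three stronger things:

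- **That no outcome assessor is blinded and the bias protection is absent altogether.** The points above rule that out.
- **That the sonographer necessarily reads bore off the image.** The Protocol measures catheter diameter there, but the SAP takes it from the specification, so this is not established.
- **That sorting the data into two groups makes blind analysis of four configurations impossible.** Two coded groups fit the two randomised gauge groups, and a length code can be carried within participant.

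**Conclusion.** The concern holds in a limited form. As written, blinding to gauge is not credible for staff who inspect or access the device, nor blinding to length for the sonographer. The analyst's masking to gauge fails if the file carries both C/V ratio and vessel diameter under the SAP rule. The blinding sections also conflict with the open-label label in the same documents.

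The effect on results cannot be quantified. Per reclassified catheter it lies between 0 and 5 points of 72-hour patency for a configuration, or 0 and 2.5 points for a gauge group, with the upper end reached only if the rescued catheter then lasts to 72 hours. The primary analysis is log-rank and Cox on time, so these figures illustrate scale; they are not estimates of bias in the hazard ratio.

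The conclusion assumes that the coloured parts are visible when the device is inspected or accessed, which follows from the absence of any masking step. It should be corrected because it changes what the gauge comparison can claim.

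**What to change.** Rewrite Protocol 6.5.2 and SAP 2.3.2 together:

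1. Reconcile the open-label description with the blinding section, and say that allocation is concealed until insertion only.
2. State by role and by outcome who is masked to gauge and who to length, naming the roles that flush, draw, time the fill, score the site and read the scans.
3. Unless masking is added, describe flush and draw failure, fill time and site score as unblinded to gauge, and sonographic readings as unblinded to length.
4. Withhold C/V ratio or vessel diameter from the masked file, or call that analysis unblinded to gauge. The SAP 5.2.2.4 models use the ratio and not vessel diameter, so withholding vessel diameter is the easier choice. It leaves a hint, since a baseline ratio above 35.3% points to 20G given the entry minimum. Withholding the ratio removes the hint but delays those models until the code is broken.
5. Use the rescue-attempt counts already planned in Tables A.7.1 and A.7.2 to compare persistence by gauge.

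Covering the coloured parts is optional. It suits this study only where it does not obstruct Luer checks, site inspection or securement: an insecure Luer connection is a recorded failure mode, securing it is a rescue step, and dislodgement is an endpoint. A cover would hide gauge only.

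The cost is protocol and SAP wording, one change to the analysis file, and one extra comparison from data already collected.

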6.5.2.1 Procedures for Unblinding

In the unlikely scenario of a SAE, the study manager or post-doctoral research fellow will open the duplicate envelope located in the locked cabinet of the CTU that has the randomization number written on the outside and contains the corresponding code within. The information will be provided to any personnel that require the information (e.g., the study Medical Doctor) as deemed necessary by the Principal Investigator.

7 STUDY PROCEDURES AND ASSESSMENTS

7.1 Venipuncture-blood collection

Blood obtained via venipuncture at screening will be collected into vacutainer tubes (2mL (waste tube), 2mL BD Vacutainer® EDTA, 1.8mg/ml-1; 6 x 2.7mL BD Vacutainer® Citrate, 109 mol/m3; Becton Dickinson, USA; total volume: 20.2 mL) for assessment of inclusion and exclusion criteria (e.g., platelet aggregation, coagulation). During the study, blood will be collected from a prominent antecubital vein of the participant's non-dominant arm using a 21G needle and collection set; Becton Dickinson, USA), and a Luer-Lok™ access device and vacutainer tubes (2mL (waste tube), 2mL BD Vacutainer® EDTA, 1.8mg/ml-1; 6mL BD Vacutainer® EDTA, 1.8mg/ml-1; Becton Dickinson, USA; Total Volume: 10mL). As per Infusion Therapy Standards of Practice guidelines²⁷, the application of a tourniquet will be applied prior to venipuncture but will be limited to less than 1 minute. Once the needle has been inserted and blood has begun to flow into the waste vacutainer tube, the tourniquet will be loosened to minimize the incidence of haemolysis.

7.2 PIVC- Insertion

Sonographic assessment and surface description of underlying anatomical features will be completed for lower arm cephalic veins on both arms to guide catheter insertion.

[figure not shown]

Figure 1. Vessel surface description based on ultrasound imaging. V, valve; T, termination; B, bifurcation; 1, insertion; dotted-line, vein path; arrow, direction of insertion.

Next, a PIVC will be inserted according to the Instructions For Use into the lower cephalic vein of one arm in accordance with a previously established standard operating procedure (see Appendix 16.2) of the participant by a trained phlebotomist or nurse using commercially approved devices with sonographic guidance. After successful cannulation a BD MaxZero™ needleless connector will be attached to the extension and flushed with 3-5 mL saline (0.9%, BD PosiFlush™; 306575; Becton Dickinson, USA), and site stabilized using a Tegaderm IV™ securement dressing²⁷.

7.3 PIVC-blood collection and pressure monitoring

A Luer-Lok™ access device, connected to the needleless connector, and vacutainer tubes (2mL (waste tube), 2mL BD Vacutainer® EDTA, 1.8mg/ml-1, REF 367841; 6mL BD Vacutainer® EDTA, 1.8mg/ml-1, REF 367873; Becton Dickinson, USA; total volume: 10mL) will be utilized to collect blood and ascertain blood quality (haemolysis; see Appendix 16.3 for methodology). Prior to blood collection a pressure transducer (DTXPlus TNF-R, Cat. no. 682021; Argon Medical, USA) and flush syringe will then be connected to the needleless connector and zeroed against venous blood pressure. The catheter will be flushed while collecting pressure data in real-time with a custom-designed LabVIEW© routine. Thereafter, the extension set will be clamped and pressure transducer/flushing syringe disconnected from needleless connector.

7.4 Image acquisition of indwelling catheter and cephalic vein

The insertion loci will be assessed prior to, and immediately after, insertion of the PIVC using clinically approved ultrasound with a wide-band, high frequency linear array probe from which all B-Mode, color-flow (CF), and pulse wave doppler (PWD) images will be acquired. At each visit prior to flushing and blood collection the following images will be recorded: a) three cross-sectional, B-mode images with the indwelling PIVC in view; b) three cross-sectional, B-mode images proximal to the PIVC tip; c) three longitudinal, B-mode images encompassing close to the insertion point of the PIVC to beyond the PIVC tip; and d) a 15 s longitudinal, PWD-CF duplex cine loop with the sample volume set ~1cm proximal to the PIVC tip. The sampling frequency for all images will be chosen high enough to avoid frequency aliasing. Coded harmonic imaging will be utilized for all images to improve visual clarity via enhancement of near-field resolution.

7.4.1 Blood flow velocity

A 15 s longitudinal, PWD-CF duplex scan positioned 1 cm past the tip of the PIVC will be utilized for the measurement of blood flow velocity. The PWD sample volume will be positioned at the center of the vein with the axial dimension set to between the upper and lower boundaries of the vessel diameter during data acquisition. Due to variations in echogenicity between participants, the gain will not be kept constant for PWD and CF image acquisitions. The velocity spectrum boundary will be traced and the velocities in the area underneath utilized for subsequent calculations (i.e. maximum and mean velocity of 5 seconds of data).

7.4.2 Angle of insertion, catheter length in vessel

Calculation of the angle of insertion, and catheter length in vessel will be achieved via assessment of the three longitudinal, B-mode scans to be taken where the probe is positioned in-line with the superior surface of the PIVC tip. These measurements (superior and inferior angles) will be taken with the internal calculations of the clinically approved ultrasound. The data will be reported as the average of the values taken from the three images.

